importance of keeping information shared within the group private at the beginning of the study and throughout each group session. Participants will be required to agree to keeping other participants' information private and confidential before joining the group sessions. At the start of group sessions, participants will also be reminded that they do not have to share any personal information during the group and may decline to answer any questions. Group sessions will occur in a private room at the Ruth Ellis Center.

Minimizing potential for undue influence. Any study that pays a stipend may engender undue influence. Eliminating this possibility by not awarding stipends would make it impossible to conduct many studies, and would shortchange participants who provide time and energy, and may incur costs such as bus, Lyft/Uber, taxi, or car fares. The resolution of this problem is to ensure that stipends are not inappropriately large, to probe potential subjects to make sure they have not been coerced, and to give persons who may have been coerced the opportunity not to enroll in the study in a manner that will protect them from retribution by the person coercing them. The group session study visit stipends proposed are in use in similar HIV prevention studies and have been reviewed by our own and other IRBs for potential undue influence.

In addition to typical incentives for completing study activities, this study includes a microeconomic intervention. The \$1,200 microgrant is in alignment with the first stimulus check and MPI [name]'s promising NIH-funded pilot study (a similar microeconomic intervention that provided group sessions and a microgrant to African American youth in Baltimore), which serves as the basis for the current project. The microgrant funds associated with the *Secure* program will not be advertised during recruitment. The \$250 in emergency assistance funds that will be provided to participants is an existing community service that is available regardless of participation in this study.

IX-4.3. Potential benefits of the proposed research to the subjects and others

Potential benefits include the following: First and foremost, all participants will receive a referral list of services in the Detroit metro area. Participants may improve their engagement in HIV prevention or HIV care as a result of their participation in the study, which could have a positive impact on their health. Participants are also provided with the opportunity to spend time talking about feelings and experiences, and they may gain insight into gender affirmation and HIV services. Additionally, the professionalization content and microgrant funds provided by the Secure program may help participants initiate microbusiness development and improve personal financial status. Participants in our previous studies have indicated that they benefited from the opportunity to participate in group-based research studies with other BIPOC trans women, and that the prospect of providing information for the possible future benefit of BIPOC trans women was motivating for them. Furthermore, participants in our prior research projects have indicated a desire to be contacted for future studies, indicating the positive opportunities participation may provide. Given that the risks to subjects are considered to be minimal, the riskbenefit ratio is deemed favorable. Study procedures are carefully developed and followed to minimize risks. The potential social and psychological risks to participants described are reasonable given the need to test culturally-relevant evidence-based microeconomic interventions to improve engagement in the HIV continuum of prevention and care among BIPOC trans women.

IX-4.4. Importance of the knowledge to be gained

The proposed study has the potential for high public health impact by evaluating the acceptability and feasibility of an adapted, evidence-based microeconomic intervention to

address health outcomes among a highly vulnerable and overlooked population disproportionately impacted by HIV. Our focus on BIPOC trans women is in line with the prioritization of sexual and gender minority communities for health disparities research, as well as the strategies of the new EHE plan for ending the U.S. HIV epidemic. Findings also have the potential to provide a "blueprint" to guide future intervention implementation efforts with BIPOC trans women who are often embedded in close-knit communities with few existing services. Given the substantial health risks associated with documented inequities in HIV outcomes and the relatively minor risks to participants, the importance of the potential knowledge to be gained relative to the participant risk is favorable.

IX-5. Study Withdrawal and Discontinuation

A participant may be discontinued from the study at any time if the participant, the MPIs, or the Sponsor feels that it is not in the participant's best interest to continue. All participants are free to withdraw from participation at any time, for any reason, specified or unspecified, and without prejudice. Reasonable attempts will be made by the investigator to provide a reason for participant withdrawals. The reason for the participant's withdrawal from the study will be specified in the study records.

The following is a list of possible reasons for early study termination:

- Participant withdrawal of consent.
- Participant is not compliant with study procedures.
- Participant relocates outside of study geographic area.
- Adverse event, inclusive of participant distress, that in the opinion of the investigator would be in the best interest of the participant to discontinue study participation.
- Protocol violation requiring discontinuation of study participation.
- Participant creates a hostile environment for study staff.
- Sponsor request for early termination of study.

X. Data Safety and Monitoring Plan

X-1. Safety and Monitoring

The study MPIs [name] and [name] will conduct oversight of internal monitoring of participants' safety and data integrity. The MPIs will also be supported by Co-Investigators [name] and [name] who will participate in the development and administration of the data and safety monitoring plan. The study team has extensive experience with HIV prevention clinical trials. The MPIs are experienced at training study staff in handling sensitive and confidential data and in the handling, storage, and processing of confidential data. Certain routine administrative, personnel, physical security, information management, and computer system or network security practices are always in place given the U-M policies.

Given the relatively low level of risk involved for participants, we do not plan to have a data safety and monitoring board (DSMB) per NIH guidelines. However, in any case we will monitor for any serious adverse events caused by study participation and report them to the U-M IRB and NIH as appropriate and as described below. We will have several mechanisms to ensure data integrity.

X-2. Contents of Monitoring

Monitoring is done of all procedures to ensure that they conform to the approved protocol; of unforeseen circumstances that might arise and affect safety; of all reports of serious adverse events as defined in 38 CFR 46 and the FDA 312.32 (death, life-threatening experience, new or prolonged hospitalization, persistent or significant disability/incapacity); of other significant adverse events (adverse events that lead to drop out by participant or termination by the investigator, or medical treatment needed to prevent withdrawal); of unexpected adverse events resulting from the study; of expected adverse events; of unanticipated problems involving risk to participants; of serious or continuing non-compliance; and of protocol violations. (See "Adverse Event and Unanticipated Problems Log" Appendix.)

X-3. Frequency of Monitoring

Data and safety monitoring will be a component of regularly scheduled weekly meetings with the study team. Meetings will involve a review of collected data (including adverse events, unanticipated problems, and participant withdrawals) to determine whether there is any change to the anticipated benefit-to-risk assessment of study participation and whether the study should continue as originally designed, should be changed, or should be terminated. MPIs will ultimately be responsible for participant safety, protocol violations, and ongoing evaluation of the study's progress. If necessary, MPIs will make appropriate recommendations for changes in protocol. The U-M IRB will conduct the monitoring at the continuing reviews as scheduled, whenever modification requests are considered, and upon receiving reports of adverse events (AEs) and serious adverse events (SAEs) from the MPIs or anyone else. The NIMH PO will monitor the study upon receipt of annual progress reports and whenever other information is received.

X-4. Adverse Events

We define AEs and SAEs as follows: An AE is any unfavorable and unintended diagnosis, symptom, syndrome or disease which either occurs during the study, having been absent at baseline, or if present at baseline, appears to worsen. AEs will be reported regardless of their relationship to the study intervention. An SAE is any adverse event that results in death, is life-

threatening, or places the participant at immediate risk of death, requires or prolongs hospitalization, causes persistent or significant disability or incapacity, or any other condition which study MPIs deem to represent significant hazards.

X-5. Reporting Plan

All AEs and SAEs will be reported regardless of their relationship to the study intervention. The study team will document all AEs and unanticipated problems. We will detect AEs and SAEs during participant visits and via survey responses and exit interviews. Any serious adverse events that are observed and/or reported will be immediately reported to [name]. We will report all AEs and SAEs by alerting the U-M IRB. The U-M PI or Project Director will prepare the appropriate IRB documentation and review it with MPIs and determine severity and relation to study participation. As for all clinical trials, these events will be classified along the following dimensions: 1) severity; 2) whether it was expected or not; and 3) the extent to which it was related to study participation. A report detailing all AEs and SAEs will be submitted to the U-M IRB. SAEs will require expedited reporting (i.e., within 24 hours of the PI becoming aware of the SAE). For events that are judged to be ongoing, the Project Director, PI or Co-I will make weekly calls to the participant to collect updated data regarding the event. This process will continue until the PI determines that the event is terminated, at which time a follow-up report will be submitted to the U-M IRB.

MPIs will promptly inform the NIMH PO and IRB of any changes in recruitment or in the protocol relevant to safety as the study is being performed. MPIs will notify the NIMH PO of any actions taken by the IRB during continuing study review and of any major changes in the status of the ongoing protocol that would only occur with IRB approval. Such changes would include but are not limited to: amendments to the protocol, temporary suspension of participant accrual or of the protocol, any changes in informed consent or IRB approval status, termination of participant accrual or of the protocol, or other problems or issues that could affect the human subjects in the study. SAEs, unanticipated problems involving risk to participants or others, and AEs will be reported the NIMH PO within 10 business days of MPIs learning of the event. Deaths related to study participation will be reported within 5 business days of learning of the event by MPIs to the NIMH PO. Any serious or continuing noncompliance concerns will be reported to the NIMH PO within 10 business days of the IRB determination and suspension, or termination of IRB approval will be promptly reported to the NIMH PO within 3 business days of receipt. The NIMH PO will be provided copies of these reports and informed of any actions taken by the IRB because of such events. As mandated by law, we will notify officials if a participant reports intentions to harm him/herself or others, or reports child abuse or abuse of an elder. In the event a participant were to report a need or interest in treatment for psychiatric disorder, or distress, an appropriate referral to resources will be provided based on an extensive list of referral resources maintained at the Ruth Ellis Center. All events and protocol violations related to the study will be reported annually in the Progress Report sent to the NIMH PO.

X. List of Appendices / Study Documents

- Recruitment materials
 - Social media post
 - Print flyer
- Eligibility screener script
- Eligibility screener survey
- Informed Consent Script
- o Informed Consent Document
- Randomization Survey
- Baseline Survey
- o Group Sessions
- Group Session Feedback Survey
- o Microgrant Disbursement Form
- Emergency Assistance Disbursement Form
- Follow Up Survey
- Exit Interview Guide
- o Secure Group Session Facilitator Guide
- Suicide Risk Assessment
- Detroit Area Resources

XI. Amendments

This space in the protocol will be used to document any future amendments.

XI-1. Ame00148836

This amendment includes minor changes to the eligibility screening survey and eligibility screening script, the baseline and follow up surveys, and the exit interview guide. We have also added two documents in Section 44: a template to capture any social harms reported by participants throughout the course of the study that do not rise to the level of an adverse event, and a post-group session facilitator fidelity and feedback survey that will be completed by intervention facilitators (not participants) after each group session. These changes and justification for each proposed change are described below. The study protocol has not been updated, as the proposed changes do not alter the procedures described in the study protocol.

In Section 8-1. Recruitment, we have made a minor update to the Eligibility Screener Script to make sure participants are aware that we will ask them about their identity, income, and sexual behavior in the eligibility screener. Also in Section 8-1 we have updated the Eligibility Screening Survey to remove the question that asks participants about HIV status, because HIV status is not an eligibility criterion (the study is HIV status-neutral and includes those living with HIV, those not living with HIV, and those who are unsure of their status), and in response to feedback that community members are not comfortable answering this question until after they have completed the informed consent process.

In Section 29.1, we have made updates to the Baseline Survey and Follow Up Survey. None of the constructs measured have been changed, though we altered some of the measures used to assess the constructs to align more closely with other NIH network studies. We also cut some items because in testing the survey was taking more than the allotted time as described in the consent form. Lastly, we made minor edits to the exit interview guide, to make questions more open-ended, and to ensure we are learning about any potential social harms participants may have experienced that were not reported to facilitators or the research team previously.

Lastly, in Section 44. Additional Documents, we have included a template on which any social harms reported by participants due to their participation in the study (e.g., losing their microgrant funds) that do not rise to the level of an adverse event will be recorded. Additionally, we have added a post-group session facilitator fidelity and feedback survey to Section 44. This survey will not be taken by participants, but instead used by facilitators to indicate fidelity to and feedback regarding group session content. Lastly, track changed documents of all documents updated in this amendment have been uploaded to Section 44.

XI-2. Ame00156620

This amendment is to update the study team (Section 1.3), adding research staff member. They will both assist with data management.

XI-3. Ame00157187

This amendment is to update the study team (section 1.3), adding a research staff member. They will assist with analyzing exit interview data.

XI-4. Ame00160383

This amendment is to reduce the number of intervention group sessions and remove the exit interview received by the waitlist control group (described in the protocol, Section 5.1.1).

We propose to reduce the number of group sessions provided to the waitlist control condition from 12 sessions to 5 sessions. All waitlist control participants are currently receiving the intervention. They have received a majority of the intervention components, including four group sessions, connection to a mentor for mentorship, and the microgrant payments totaling \$1,200 to invest in their business or other professional development goals.

NIH originally funded this study as an RCT where the control condition received only standard of care, which consists of programs currently available in community settings. We proposed and received approval from NIH to alter the study design so that we also provided the SeCuRE intervention to the control group using a waitlist design, and planned to use PI's discretionary funds to cover the additional expenses. We have now completed all research activities that were originally proposed to and approved by NIH – that is, we completed enrollment, the intervention condition received the SeCuRE intervention and completed an exit interview, and all participants completed the baseline and follow up surveys.

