Trans women represent one of the populations at highest risk for HIV infection.³³ Approximately 19-21% of trans women in the US are living with HIV. 14-16 Evidence suggests substantial racial/ethnic inequities in HIV with Black, Latina, and other trans women of color representing the majority of the cases among trans women. 17,18,34 The HIV Prevention and Care Continuum frameworks emphasize the need for reducing HIV transmission and acquisition risk via consistent condom use, regular HIV testing, pre-exposure prophylaxis (PrEP) among HIVnegative individuals, and engagement and retention in HIV care in addition to uptake, adherence, and persistence to antiretroviral therapy (ART) to achieve virologic control among persons living with HIV. 35-37 There are notable inequities in HIV prevention and care continua outcomes among BIPOC trans women.^{38,39} For example, evidence suggests that BIPOC trans women have a 40% lower odds of lifetime HIV testing and 50% lower odds of HIV testing in the past 12 months compared with gay/bisexual men.⁴⁰ Studies also indicate very low PrEP uptake (3 to 32% use among PrEP-eligible trans women), 41,42 and low rates of virologic control (68 to 70%) among trans women living with HIV. 38,43-52 Thus, interventions are needed that address inequities across both the HIV prevention and care continuum among BIPOC trans women in the US.38,51,52

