In line with recommendations by NIH and the research methods literature, given the sample size and intent of the pilot study we will not conduct a formal test of outcomes or attempt to obtain an estimate of effect size. $^{123-136}$ We will consider engagement in HIV prevention and care as an exploratory outcome defined as PrEP use and \geq 80% adherence among those not living with HIV and suppressed HIV viral load among those living with HIV, collected via self-report. These analyses will be conducted as a feasibility check to ensure all measures required to construct the primary outcome and that moderators and mediators for a larger formal RCT are present and will yield analyzable data.

VI-4. Analytical Design

VI-4.1 Acceptability & Feasibility analyses. The principal analytical aim of the pilot RCT is to measure feasibility and acceptability and evaluate whether feasibility and acceptability benchmarks are met. To fulfill this objective, frequency tables for all variables and measures of central tendency and variability for continuous variables will characterize the sample and quantify the intervention feasibility and acceptability outcomes. We will address incomplete data via direct maximum likelihood estimation (MLE) or multiple imputation (MI)¹⁵⁰ assuming that incomplete data arise from a conditionally random (MAR) mechanism¹⁵¹ and include sensitivity analyses to evaluate the robustness of the MAR assumption. The proposed analyses will be conducted using validated algorithms in the general purpose statistical programs SAS or Stata. All statistical software programming code will be fully documented to enable future code review, transparency, and results reproducibility.

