VI-4.2 Exploratory analyses. To fulfill our secondary goal of generating preliminary effects of the intervention on the primary HIV serostatus-neutral HIV prevention and care engagement outcome, proportions of the outcome will be plotted by group over time to describe overall patterns of change across time in the *Secure* intervention group and the control group. Hypothesis testing will be de-emphasized in line with NIH¹⁵² and research methods literature cautions^{153,154} regarding the instability of inferential results from small-scale pilot studies. With that caveat, we anticipate that following the *Secure* intervention, intervention participants will exhibit higher odds of the HIV prevention and care outcome relative to control group participants in a time-averaged comparison of the post-baseline intervention and control groups' outcome proportions. This exploratory comparison will be performed at alpha=.05 in a generalized linear mixed model (GLMM) suitable for this binary outcome. Repeated observations from each participant will be the unit of analysis. Alpha will be set at 5% for this exploratory analysis.

VI-4.3 Power analyses. Although the main purpose of this study is to determine preliminary feasibility and acceptability and to visualize changes in outcomes and mechanisms of change over time rather than to perform formal hypothesis tests, we conducted several power analyses using NCSS PASS 21 156 to supply additional information. Assuming power=.80, α =.05, and N=32 participants available at the last follow-up, we computed confidence interval widths for a) proportions for binary variables and b) means for continuous variables measuring feasibility and acceptability. For example, for the study enrollment proportion, assuming α =.05, power=.80, and

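### VI-4.2 names no covariates for a composite that is a different event by HIV status; one adjusted exploratory contrast would be a cheap gain in precision

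*Combined protocol and SAP*

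**What the plan says.** Section VI-4.2 (Exploratory analyses) sets a "secondary goal of generating preliminary effects of the intervention" on the serostatus-neutral HIV outcome. The arms are to be compared "in a time-averaged comparison of the post-baseline intervention and control" groups, and "This exploratory comparison will be performed at alpha=.05 in a generalized linear mixed model (GLMM) suitable for this binary outcome". Repeated observations per participant are the unit of analysis. No covariates are listed, and the text does not say how the baseline value of the outcome enters the model.

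Section VI-3 defines the outcome as PrEP use with at least 80% adherence for participants not living with HIV, and "suppressed HIV viral load among those living with HIV, collected via self-report". Target outcomes are measured at baseline, after the program and three months later. Section III gives background rates: "very low PrEP uptake (3 to 32% use among PrEP-eligible trans women") and "low rates of virologic control (68 to 70%) among trans women living with HIV". It puts HIV prevalence among US trans women at 19-21%.

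Section VII-4.4 describes 1:1 randomization after enrollment activities are complete and mentions no stratification. The Randomization Survey appendix is not available to check. Section VI-4.3 plans on "N=32 participants available at the last follow-up".

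**The concern.** Two events with very different background rates are pooled into one binary outcome, so HIV status should be a strong predictor of it. The baseline value of the composite should also predict later values, because people tend to stay on or off PrEP, and suppressed or not. A model with arm alone leaves both sources of variation in the error term. It also lets any chance imbalance in HIV share pass into the one realised contrast.

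At stake is the precision of the preliminary effects that VI-4.2 sets as its secondary goal. The primary feasibility and acceptability results do not depend on it.

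**Working it through.** **The plan's own figures.** The two descriptive figures in VI-4.3 reproduce. The exact confidence interval for 80% with N=32 is 29.8 points wide, and t(.975, 31)/√32 = .36. The minimum detectable increase for the mixed model (33.7-42.8 points) cannot be reproduced, because VI-4.3 gives neither a control rate nor a within-person correlation. That does not show it to be wrong, but it gives no basis for judging the effect of adjustment.

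**How strongly HIV status predicts the composite.** Let h be prevalence, s the suppression rate, p the PrEP rate and m = hs + (1−h)p. The share of variance explained is h(1−h)(s−p)² / [m(1−m)].
- Low end (h=.19, s=.68, p=.32): m = .388; .0199/.2375 = 8%.
- High end (h=.21, s=.70, p=.03): m = .171; .0745/.1416 = 53%.

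The PrEP range is for use without the adherence condition, so the rate of the composite's PrEP branch can be no higher.

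**Chance of imbalance.** Assume no stratification, and let X₁ and X₂ be independent binomials with 20 per arm. A 20-point gap is 4 people.
- P(|X₁−X₂| ≥ 4) = .155, .164 and .172 at prevalence .19, .20 and .21.
- In the direction that favours Secure: .078, .082 and .086.
- If 40% were living with HIV (an assumption): .258, or .129 in one direction.

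**Effect of a 20-point gap on the expected contrast, with no treatment effect.**
- Smallest: .20 × (.68 − .32) = .072.
- Largest: .20 × (.70 − .03) = .134.

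**That shift against sampling error.** Assume 20% prevalence, 69% suppression, two waves and an observed within-person correlation r. The standard error is √[2 × m(1−m)(1+r)/2 / 20].
- PrEP 32%: m = .394. With r=.7 the SE is .142, the shift is .20 × .37 = .074, and the ratio is about 0.5.
- PrEP 18%: m = .282. With r=.3 the SE is .115, the shift is .20 × .51 = .102, and the ratio is about 0.9.

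**Gain from adjustment.** The adjusted analysis regresses each person's mean post-baseline outcome on arm, baseline composite and HIV status. It was simulated under no effect with 20 or 16 per arm, two complete post-baseline waves, 69% suppression, an HIV share of 20% or 40%, and latent within-person correlations of .3, .5 and .7. The correlations and the 40% share are assumptions.

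| PrEP rate | Variance ratio, adjusted/unadjusted | Variance removed |
|---|---|---|
| 18-32% | .50-.86 | 14-50% |
| 3-10% | .26-.55 | 45-74% |

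Null rejection was 2.1-4.8%. A separate set of 1,000 runs per scenario gave ratios of .51-.89 at PrEP 18-32%, with null rejection of 2.9-5.2% (mean 4.0%). A third check used a random-intercept model with 32 participants. There the SD of the difference fell by 6-30%, which is a variance reduction of 1−.94² = 12% to 1−.70² = 51%.

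**Why not put the covariates in the GLMM.** An adjusted GLMM, with a linear fallback for separation, rejected a true null in 6.7% of runs on average at PrEP 18-32%, against 5.6% for the unadjusted GLMM. With 16 per arm and PrEP at 3%, the adjusted GLMM was separated in 38-68% of runs. The linear model avoids both problems and needs no conditional rule.

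**The case against.** The strongest case against is that nothing here is broken. The trial's purpose is descriptive, hypothesis testing is de-emphasised, and VI-3 says "we will not conduct a formal test of outcomes or attempt to obtain an estimate of effect size". An adjusted contrast adds machinery to a comparison that the plan plays down. A 20-point gap in HIV share is a tail event, and at PrEP 18-32% it moves the contrast by less than one standard error, which ordinary uncertainty already covers. All of this stands, and it limits the point to an optional improvement.

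Three further objections also stand in part.
- **Scale.** VI-4.2 speaks of odds, while the gain shown is for a difference in proportions. For the log odds ratio from an adjusted GLMM with 32 participants, the empirical spread fell by only 5-16% in seven of eight scenarios and rose by 4% in the other.
- **Justification.** The different-event argument supports HIV status only. The baseline composite rests on within-person persistence. Where persistence is strong, HIV status adds little beyond it.
- **Timing.** Amendment Ame00160383 (XI-4) reports that the baseline and follow-up surveys are complete, so covariates named now do not precede data collection.

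A reader might infer that the unadjusted comparison is biased, or that the plan rules out adjustment. The documents support neither. Randomization makes the unadjusted contrast valid on average, and covariates are unspecified, not excluded. Nor do the documents show that the arms are in fact unbalanced.

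**Conclusion.** The point holds as a cheap improvement to an exploratory analysis. VI-4.2 compares the arms on an outcome that is a different event by HIV status and names no covariates, although two strong predictors should be available without new data. With 20 per arm there is a 16-17% chance of a gap that shifts the expected contrast by 7-13 points. Adjustment removes about 14-50% of the variance of the difference in proportions at PrEP 18-32%, and more at lower rates, with null rejection at or below about 5%.

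These figures rest on background rates rather than this sample's, on assumed correlations, on unstratified allocation and on complete waves. That HIV status is recorded at baseline is inferred. The first amendment (XI-1) removed the question from the screener because people preferred to answer after consent, and the baseline survey follows consent.

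Two neighbouring matters are separate points and add no weight here: the composite has no stated branch for participants who do not know their status, and VI-3 and VI-4.2 differ on whether effects will be estimated.

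**What to change.** Keep the planned unadjusted GLMM. Add to VI-4.2 one exploratory adjusted contrast, reported whether or not the arms turn out balanced:

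- **Outcome:** each participant's mean of the composite over the post-baseline waves.
- **Model:** linear regression on arm, baseline composite and baseline-reported HIV status (living with HIV versus not known to be), with HC3 standard errors.
- **Reported as:** a difference in proportions with its confidence interval, labelled exploratory.
- **Missing waves:** the multiple imputation that VI-4.1 already allows, with a sentence in VI-4.2 extending it to this analysis.
- **Date:** state when the text was added. If outcomes have already been analysed by arm, label the adjusted contrast as added later.

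The cost is a few lines of text and no new data. The downsides are two extra parameters, sparse cells (16 × .20 = about 3 people per arm living with HIV at N=32), and a somewhat conservative test when PrEP use is very low. The simulations had no missing waves, so the gain after imputation has not been measured.
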